7.1.2 Non-serious Adverse Event

A non-serious AE is any event that does not meet the above-mentioned SAE definition.

7.1.3 Severity

The severity of each AE will be determined based upon the following criteria:

Mild: Transient symptoms, no interference with subject's daily activities. Less than 48 hours, no medical intervention/therapy required.

Moderate: Marked symptoms, moderate interference with the subject's daily activities. No or minimal medical intervention/therapy required.

Severe: Considerable interference with the subject's daily activities. Medical intervention/therapy required; hospitalization possible.

7.1.4 Relationship to Study Medication

The relationship to study medication will be determined and recorded on eCRF by an Investigator using the following criteria based on the World Health Organization (WHO) classification:

Causality	Definition
Unrelated	Concurrent illness, concurrent medication, or other known cause is clearly responsible for the adverse event OR based upon available information regarding subject history, disease process, relationship of adverse event to dosing, and drug pharmacology, a relationship between the drug and adverse event is unlikely.
Possible	The adverse event follows a reasonable sequence from the time of drug administration, but could also have been produced by the subject's clinical state or by other drugs administered to the subject. Event with a time to drug intake that makes a relationship improbable (but not impossible). Disease or other drugs provide plausible explanations
Probably	The adverse event follows a reasonable sequence from the time of drug administration, follows a known response pattern of the study treatment class, is confirmed by improvement on stopping the study treatment is the most likely of all causes. Event with reasonable time relationship to drug intake: 
• Unlikely to be attributed to disease or other drugs• Response to withdrawal clinically reasonable• Rechallenge not required
Definite	The adverse event follows a reasonable sequence from the time of drug administration, follows a known response pattern of the study treatment class, is confirmed by improvement on stopping the study treatment, and there is no other reasonable cause exists.

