4.7 Stopping Rules

4.7.1 Individual Stopping Criteria

The following stopping criteria should be applied for individual subjects who experience one or more of the following spontaneously-reported adverse events:

- Loss of consciousness, hypotension (blood pressure <90 mmHg systolic and/or <60 mmHg diastolic, or a decrease of ≥20 mmHg from pre-dose), ischemic colitis, and severe hypersensitivity reactions/anaphylaxis should result in immediate discontinuation.
- Severe, treatment-related cases of diarrhea, tachycardia, chest discomfort/chest pain, and dyspnea should result in discontinuation.

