4.7.2 Overall Study Stopping Criteria

The study will be stopped if at least 2 subjects experience the same treatment-related, life-threatening event.

Draft

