8.6.2 Adverse Events

The original terms used in the eCRF by Investigators to identify AEs will be coded to MedDRA® system organ class and preferred terms. Adverse events will be summarized in terms of incidence per dose group and overall. The incidence of an AE is defined as the number of subjects who experienced at least one episode during the study. Adverse event incidence rates will be summarized by system organ class (SOC) and preferred term (as determined by the coding).

Whatever the level of classification, if a subject experiences multiple episodes of an event within the given time reference, then the event is only counted once. Further, for summaries by severity or causality, the most severe event is chosen for a subject if that subject experiences multiple episodes of the same event

AEs with onset dates between consent and prior to administration of the first dose of study medication or after the last day of treatment + 7 days will be considered non-treatment emergent, and excluded from the tabulations. Events with completely or partially missing onset dates will be included in the tabulations unless the available partial date information clearly indicates that the event happened outside of the treatment period.

P-values from Fisher's exact test or chi-square test will be presented in the AE summary tables. The test will be performed to compare incidence rates between the sprinkle and capsule formulations of lubiprostone and the matching placebo group.

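### An event with doubtful timing fits both Unrelated and Possible, and the causality summary keeps the most severe episode rather than the most related one, so treatment-related adverse events can be misclassified

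*Combined protocol and SAP*

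**What the plan says.** Section 7.1.4 has the investigator grade each event as Unrelated, Possible, Probably or Definite, "using the following criteria based on the World Health Organization (WHO) classification".

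- **Unrelated** has two limbs. One is a clear other cause. The other is a judgement from history, disease, timing relative to dosing and pharmacology that "a relationship between the drug and adverse event is unlikely".
- **Possible** opens with "The adverse event follows a reasonable sequence from the time of drug administration, but could also have been produced by the subject's clinical state"; another medication is a further alternative cause. It then adds an "Event with a time to drug intake that makes a relationship improbable (but not impossible".

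No level lies between these two.

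Section 7.1.3 defines severity on its own scale of mild, moderate and severe. For repeated episodes, Section 8.6.2 states that "for summaries by severity or causality, the most severe event is chosen for a subject if that subject experiences multiple episodes of the same event". No other rule for causality summaries appears.

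Two stopping provisions depend on relatedness. Section 4.7.1 states: "Severe, treatment-related cases of diarrhea, tachycardia, chest discomfort/chest pain, and dyspnea should result in discontinuation". Section 4.7.2 stops the study if "at least 2 subjects experience the same treatment-related, life-threatening event". No section says which of the four grades make an event treatment-related.

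Section 2.2.2 lists the adverse event endpoint as incidence by system organ class and preferred term. Causality is not part of it.

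**The concern.** There are two separate faults.

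The first is in the grading. Two investigators can agree on the facts of an event and on how doubtful its timing is, follow the same table, and record different grades. About 70 sites will use that table. This is not ordinary variation in judgement, because the table itself returns two answers.

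The second is in the tabulation. Severity and causality are different axes, and the rule selects on severity for a summary that reports causality. A milder but more strongly related episode then disappears from that summary.

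At stake are the causality tabulations and, through the grading overlap, the events that count toward the treatment-related conditions in Sections 4.7.1 and 4.7.2.

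**Working it through.** The plan gives no figure on this point, so there is none to reproduce. The check compares the texts and then counts combinations on the plan's own scales.

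**Step 1: grading (Section 7.1.4).** Take an event with no clear other cause, whose onset relative to dosing makes a drug cause doubtful but not excluded.

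| Text applied | Result |
|---|---|
| Unrelated, second limb: timing is weighed and a relationship judged unlikely | Met |
| Possible, timing sentence: improbable, not impossible | Met |
| Possible, opening sentence: reasonable time sequence | Not met |

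The event fits two grades, and the two sentences under Possible disagree about it. An event doubted only on history or pharmacology, with unremarkable timing, does not meet the timing sentence. This overlap therefore covers timing-based doubt only.

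**Step 2: repeated episodes (Section 8.6.2).** Example: one subject has a severe Unrelated episode of diarrhea and a mild Definite one. The most severe episode is kept, so the causality summary shows Unrelated.

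To see how general this is, consider two episodes of the same event, each with one of 3 severity grades and one of 4 causality grades:

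- States per episode: 3 × 4 = 12. Ordered pairs: 12 × 12 = 144.
- Severity differs in 3 × 2 = 6 ordered severity pairs, each with 4 × 4 = 16 causality pairs: 6 × 16 = 96. Severity ties in 3 × 16 = 48.
- Where severity differs, the more severe episode is the less related one in 6 of the 16 causality pairs: 6 × 6 = 36 of 144 (25%).
- Where severity ties, causality differs in 12 of the 16 pairs: 3 × 12 = 36 of 144 (25%). The rule does not say which episode to keep.
- The remaining 144 − 36 − 36 = 72 agree with a rule that keeps the most related episode.

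Now assume, since the plan does not define it, that every grade except Unrelated counts as related:

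- A subject with a related episode is shown as Unrelated in 6 × 3 = 18 of 144 (12.5%).
- The result is undetermined in a further 3 × 6 = 18 of 144 (12.5%).

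Under a most-related rule, no combination keeps the less related episode and none is undetermined. All of these are counts of logical combinations, not expected event rates.

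**Step 3: reach.** Section 8.6.2 counts a subject once per term whatever the causality, so incidence by system organ class and preferred term does not change. The summary rule acts on tables after grading and cannot affect Sections 4.7.1 or 4.7.2. The grading overlap can, because those sections depend on relatedness and name no grades.

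**The case against.** The strongest case on the other side is that this is a wording matter with a narrow effect. Much of that stands.

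- The summary rule misleads only when one subject has repeated episodes of the same event with different causality grades, and the less related one is the more severe. Treatment-emergent events are limited to the 7 treatment days plus 7 more.
- Grading is done under a double-blind, double-dummy design, and nothing in the documents shows a bias between arms.
- Deaths, serious events and discontinuations due to adverse events are listed individually (Section 8.6.1). Serious events are reported within 24 hours whatever their causality (Section 7.2.1).
- The first group of events in Section 4.7.1 carries no relatedness condition.

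Two defences do not stand. It could be said that most severe is shorthand for most related, but the sentence names both summaries and gives one rule, so a programmer would select on severity. It could also be said that the SAP, which Section 8 says will further outline the analyses, will settle the matter. It could correct the tabulation, but not grades already recorded under an ambiguous table.

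A reader might also infer more than the documents support:

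- **That a safety endpoint is compromised.** The listed endpoint does not use causality.
- **That a causality table serves to compare sprinkle with capsule.** No section gives it that purpose; the tests in Section 8.6.2 set the two formulations against placebo.
- **That every event judged unlikely fits two grades, one related and one not.** The overlap is limited to timing, and treating Possible as related is an assumption.
- **That the summary rule could decide whether the study stops.** It plays no part in that decision.

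**Conclusion.** Both faults are in the text as written, and no other section corrects them. Treatment-related adverse events can be misclassified in the causality tabulations; the documents do not show that they will be. The overlap can move an event in either direction. Where severity differs, the summary rule can only lower reported relatedness compared with a most-related rule. Where severity ties and causality differs, it gives no answer.

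The effect on actual counts cannot be computed, because the documents give no frequency of repeated or discordantly graded episodes. The 12.5% figures rest on the assumption that every grade except Unrelated is related. The primary analysis and the listed adverse event endpoint are untouched. The correction is worth making because the faults are clear and the cost is close to nothing.

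**What to change.** 1. **Section 8.6.2:** split the rule. Keep the most severe episode for severity summaries and the episode with the strongest relationship for causality summaries.
2. **Section 7.1.4:** place the unlikely or improbable wording in one grade only, so that the grades are mutually exclusive and Possible no longer contradicts its own opening sentence. Do this before events are graded, since later analysis rules cannot repair recorded grades.
3. **Sections 4.7.1 and 4.7.2:** reconcile the term treatment-related with the Section 7.1.4 grades, and use the same meaning in the adverse event tables. Which grades qualify, and what follows clinically, is for the sponsor to decide; no clinical rule is proposed here.

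The cost is wording in these sections and in the eCRF completion guide, plus one line of table programming. No new data are needed. The count of related events may rise slightly: the summary change can only raise it, while the effect of the grading change depends on which grade keeps the wording.

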7.1.5 Onset and Duration

The date and time the event was reported to investigator will be recorded, as well as the start date and time and resolution date and time of the event.

7.2 Recording and Reporting of Adverse Events

All AEs will be recorded in the source document and applicable eCRF(s) from the time the informed consent is signed until the end of study. AEs occurring prior to the first dose of study drug will be considered non-treatment emergent. The Investigator shall notify the Sponsor at any time when an SAE is believed to be related to the administration of study medication, even after the end of the study. At any time during the study, those events meeting the definition of an Immediately Reportable Event (IRE) must be recorded on source document, IRE Reporting Form, and applicable eCRF(s), and then reported to Sponsor or designee using the IRE Reporting Form as specified in [Section 7.2.1](#).

All AEs, regardless of seriousness, severity or presumed relationship to study medication, must be recorded using medical terminology in the source document and in the eCRF. Whenever possible, diagnoses should be given when signs and symptoms are due to a common etiology (e.g., cough, runny nose, sneezing, sore throat, and head congestion should be reported as “upper respiratory infection”). Investigators must record on the source document and eCRF their opinion concerning the relationship of the AE to study therapy and the severity of the event. All measures required for AE management must be recorded in the source document and reported according to Sponsor instructions.

For any subject who is discontinued from the study due to an AE, it is expected that the Investigator will follow the subject until the event resolves, the event returns to baseline (if a baseline value is available), or until such time that the Investigator does not anticipate any further improvement or worsening of the event.

7.2.1 Reporting of Immediately Reportable Events

The following events, regardless of severity or seriousness, are considered immediately reportable IREs and are to be reported via the IRE Form or IRE Pregnancy Report Form within 24 hours to the Sponsor or designee:

- All Serious Adverse events
- All pregnancies
- Events of Special Interest
 - Hepatotoxicity
 - Anaphylaxis, including anaphylactoid reaction and anaphylactic shock

Immediately Reportable Events, such as SAEs, should be recorded on the Adverse Event source document and eCRF. In addition, any IRE occurring during the clinical study must be reported within 24 hours to the Sponsor or designee using the IRE form. The initial report of an IRE must be documented on the study IRE form, signed by the Investigator and submitted by facsimile. The Investigator must provide the following information: protocol number, subject's initials and study number AE term and associated dates, causal relationship between the event and study medication, relevant history, study medication dosing details, full description of the event, and other required data within the IRE form. All oral reports of an IRE

must be followed immediately by a facsimile of the IRE form signed by the Investigator. Investigators should not leave oral reports of IREs on any voicemail aside from the Sponsor's Medical Monitor or designee. The details of the adverse event reporting requirement are also outlined in a safety reporting plan.

The Sponsor assumes responsibility for reporting of expedited and periodic safety reports to the appropriate regulatory authorities. The Sponsor will distribute to the Investigator any safety expedited reports that occur in this study, and in other clinical studies involving lubiprostone. The Investigator may need to report SAEs to the appropriate IRB/IEC in accordance with local regulations.

All IREs that have not resolved by the end of the study, or that have not resolved upon discontinuation of the subject's participation in the study, must be followed until either:

- the event resolves;
- the event stabilizes;
- 30 days after treatment exposure;
- the event returns to baseline, if a baseline value is available;
- the event can be attributed to medications other than the study medication, or to reasons other than study conduct; or
- the Investigator does not anticipate any further improvement or worsening of the event.

7.2.1.1 Reporting of Pregnancies

Any pregnancy occurring in a female subject after the first intake of study medication, while not an AE, is considered an IRE. It must be reported within 24 hours of the Investigator learning of the event using only an IRE Pregnancy Report Form. Any subject, who becomes pregnant, shall be removed from the clinical study. Pregnant subjects should be followed for the duration of the pregnancy and the outcome should be reported. Follow-up information regarding the outcome of the pregnancy and any postnatal sequelae in the infant up to one year of age will be required.

7.2.2 Outcome

The Investigator should follow all IREs until resolution (return to baseline status) or loss to follow-up or until no further improvement or worsening of the participant's condition is expected. Loss to follow-up implies that the Investigator site is no longer aware of the participant's whereabouts, and is unable to obtain current contact information. All attempts to contact the participant must be captured in the appropriate trial source document.

7.2.3 Symptoms of the Disease Under Study

Symptoms of the disease under study should not be classified as AEs as long as they are within the normal day-to-day fluctuation or expected progression of the disease. However, significant worsening of the symptoms should be recorded as an AE.

Endpoints and reports of events on the progression of underlying condition (such as worsening constipation and fecaloma) will be considered expected events even though these are not listed in the Investigator Brochure as expected events for study medication.

7.2.4 Clinical Laboratory Evaluations

A change in the value of a safety laboratory investigation can represent an AE if the change is clinically relevant or if, during treatment with the investigational product, a shift of a parameter is observed from a normal value to a pathological value, or a further worsening of an already pathological value. When evaluating such changes, the extent of deviation from the reference range, the duration until return to the reference range, either while continuing treatment or after the end of treatment with the investigational product, and the range of variation of the respective parameter within its reference range, must be taken into consideration.

If, at the end of the treatment phase, there are pathological laboratory values which were not present at baseline, per Investigator discretion further clinical or laboratory investigations should be performed until the values return to within reference range or until a plausible explanation (e.g., concomitant disease) is found for the pathological laboratory values.

The Investigator should decide, based on the above criteria and the clinical condition of a subject, whether a change in a laboratory parameter is clinically significant and therefore represents an AE.

7.2.5 Vital Signs

A change in the value of a vital sign measurement can represent an AE, per the Investigator's discretion. The Investigator should decide, based on their discretion, and the clinical condition of a subject, whether a change in vital signs is clinically significant and therefore represents an AE.

7.2.6 Overdose

There are no specific treatments or monitoring guidelines prescribed for subjects with lubiprostone overdose. It will be left to the discretion of the Investigator's clinical judgment on how to provide appropriate symptomatic treatment.

Any incidences of overdose with the investigational product will follow the same reporting procedures as an AE (see [Section 7.2](#)), and only where applicable, as an IRE (see [Section 7.2.1](#)).

7.3 Contacting Sponsor Regarding Safety

Any medical safety related issue regarding the conduct of the trial needs to be addressed by the Medical Monitor. The name of the individual (and corresponding telephone numbers) who should be contacted regarding safety issues are listed on the Sponsor Contact Information page in the front section of this protocol.

7.4 Coding of Adverse Events

All AEs will be coded by the Sponsor's designee using the current Medical Dictionary for Regulatory Activities (MedDRA)® terminology.

Draft

8. STATISTICAL METHODS AND DATA MANAGEMENT

The statistical analyses described in this section will be performed for the study as further outlined in the Statistical Analysis Plan (SAP), which will be finalised prior to unblinding of the database and will be included in the Clinical Study Report for this protocol. Investigators will be provided with subject treatment allocation information associated with their study participants upon finalisation of the Clinical Study Report.

8.1 Determination of Sample Size

This is a phase 3, multicentre, double-blinded, randomized, placebo-controlled study evaluating the bioequivalence of Sprinkle and Capsule formulations of lubiprostone when administered orally in subjects with chronic idiopathic constipation. Subjects will be randomized (1:1:1 ratio) to receive either lubiprostone sprinkle, lubiprostone capsule or matching placebo BID in a blinded, double-dummy fashion.

In clinical studies of the lubiprostone capsule formulation during the CIC development program, the average observed SBM count at Week 1 for lubiprostone 24 mcg BID was 5.62 with a standard deviation of 4.24. In order to achieve the conclusion of equivalence between the sprinkle and capsule formulations of lubiprostone, the 90% confidence interval for the ratio of means has to be contained within the interval of [0.8, 1.25]. Thus, a sample size of 156 per group is required to achieve 90% power at a 10% significance level.

Assuming 10% of subjects do not meet criteria for inclusion in the Per Protocol population and/or do not have observed week 1 SBM count due to early withdrawal or other reasons, 174 subjects per treatment group (a total of 522 subjects) will be required for this study.

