8.5 Analysis of Efficacy

8.5.1 General Inferential Principles

All efficacy analyses will be conducted using the mITT and PP populations by randomized treatment group and, unless stated otherwise for equivalence analysis, all tests are two-tailed at a significance level of $\alpha = 0.10$ with 90% confidence intervals (CIs). For the superiority analysis compared Lubiprostone sprinkle and capsule formulations to the matching Placebo, all tests are two-tailed at a significance level of $\alpha = 0.05$. Analysis of covariance (ANCOVA) and the van Elteren test will be performed to compare the sprinkle and capsule formulations of lubiprostone with matching placebo.

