8.5.2 Primary Analysis of Efficacy

The primary efficacy analysis is the LDOCF SBM count at Week 1. SBM is defined as any BM that does not occur within 24 hours after rescue medication use.

For the primary efficacy variable of observed Week 1 SBM count, the 90% CIs of the treatment ratio between the sprinkle and capsule formulations will be calculated and the equivalence of the two medications can be claimed if the equivalence limits are within the interval of [0.8, 1.25].

The primary efficacy analysis will be performed in PP population.

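### Under the plan's own 90% CI rule, 156 per group gives about 80% power at best, not 90%; 90% power at 156 corresponds to an 80% CI

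*Combined protocol and SAP*

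**What the plan says.** Section 8.1 takes its planning values from earlier capsule studies: "the average observed SBM count at Week 1 for lubiprostone 24 mcg BID was 5.62 with a standard deviation of 4.24". It sets the criterion that "the 90% confidence interval for the ratio of means has to be contained within the interval of [0.8, 1.25"], and concludes: "Thus, a sample size of 156 per group is required to achieve 90% power at a 10% significance level". After a 10% allowance for subjects who are not evaluable, "174 subjects per treatment group (a total of 522 subjects) will be required for this study". The synopsis gives the same calculation.

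Section 8.5.2 applies the same rule to the primary analysis in the per-protocol population: "the 90% CIs of the treatment ratio between the sprinkle and capsule formulations will be calculated", with equivalence claimed if the limits fall within 0.8 to 1.25. Section 8.5.1 describes the general level as two-tailed 0.10 with 90% CIs.

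Neither section 8.1 nor the synopsis gives the sample-size formula, the assumed true ratio, the analysis scale, or whether the 10% is one-sided or two-sided.

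**The concern.** Requiring a 90% CI to lie inside both limits is the same as rejecting two one-sided hypotheses at 5% each. A sample size for that rule must use 5% per side and must allow for failure at either limit. The stated 156 looks too small for 90% power on that basis, and looks like the answer for 10% per side.

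The sprinkle-versus-capsule comparison is the single primary comparison (section 8.5.1.2). If its power is overstated, sponsor, sites and ethics committees accept a higher chance of an inconclusive trial than they have been told. A failed result could then be taken for a difference between formulations when it reflects the trial's size. The loose wording of the level also leaves room to argue later for an 80% CI, which would double the error rate on each side.

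**Working it through.** **Inputs**
- Mean 5.62, SD 4.24, limits 0.8 and 1.25, stated power 90%, 156 evaluable per group, 10% loss: section 8.1.
- Decision rule, 90% CI: sections 8.1 and 8.5.2.
- True ratio: not stated. I assume 1.0, the most favourable value, and also show 0.95 and 1.05.

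**Derived quantities**
- CV = 4.24 / 5.62 = 0.7544.
- Log-normal variance s² = ln(1 + CV²) = 0.4506, so s = 0.6712.
- Margin on the log scale = ln 1.25 = 0.2231, symmetric because ln 0.8 = −0.2231.
- Standard error of the log ratio at 156 per group = 0.6712 × √(2/156) = 0.0760.

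**Step 1: reproduce the plan's figure.** For two one-sided tests at level a per side with true ratio 1, the normal approximation for 90% power is

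n = 2 (z₁₋ₐ + z₀.₉₅)² s² / (ln 1.25)²

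where z₀.₉₅ appears because the 10% type II error is split between the two limits. With a = 0.10:

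n = 2 × (1.2816 + 1.6449)² × 0.4506 / 0.2231² ≈ 155.0.

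The exact t-based calculation gives 89.9% at 155 and 90.1% at 156, so the smallest n is 156. Then 156 / 0.9 = 173.3, rounded up to 174, and 174 × 3 = 522. All of the plan's figures are reproduced, but with 10% per side, which is an 80% CI.

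**Step 2: apply the plan's own rule.** With a = 0.05:

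n = 2 × (1.6449 + 1.6449)² × 0.4506 / 0.2231² ≈ 195.9, or 197 by the exact t calculation.

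Power at 156, normal approximation: 2Φ(0.2231/0.0760 − 1.645) − 1 = 2Φ(1.291) − 1 = 80.3%. The exact t value is 80.1%, and a simulation of 40,000 trials gave 80.5%. The smallest n for 80% power at 5% per side is also 156.

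**Step 3: other scales and assumptions, 5% per side**

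| Case | Power at 156 per group | n per group for 90% |
|---|---|---|
| Log-normal, true ratio 1 | 80.1% | 197 |
| Log-normal, true ratio 0.95 or 1.05 | about 71% | not computed |
| Log ratio of arithmetic means, delta method (SE = CV√(2/n)) | 66.7% normal, 66.4% with t | about 248 |
| Ratio of arithmetic means, Fieller | 65.3% | 253 |

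Negative-binomial simulations with the same mean and SD gave 65 to 66%. If all 174 per group were evaluable, log-normal power would be 85.3%. No two-sided equivalence calculation that was tried reaches 90% at 156 under the 90% CI rule.

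**The case against.** The strongest points on the other side are these.

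- **The cause is inferred.** No formula is given, and the 10% agrees with the two-tailed 0.10 in section 8.5.1. A single one-sided 5% test with the type II error not split gives 155, because z₀.₉₅ + z₀.₉₀ is the same sum as in step 1. This stands as a caution about how the error arose. It does not rescue the figure: that formula ignores one of the two limits and overstates the power of the CI rule in the same way. If 10% means two-sided 10%, the level is right and the power is wrong.
- **Baseline adjustment might recover power.** On the log scale, covariates explaining about 21% of the variance (a correlation of about 0.46) would bring 156 per group back to 90%. But neither section 8.1 nor section 8.5.2 specifies adjustment for the primary ratio, and no correlation is given. Inclusion criterion 7 also restricts baseline to below 3 SBMs per week.
- **The 65 to 67% depends on the scale.** This is correct. The plan refers to a ratio of means and to a treatment ratio without fixing a scale, so these figures hold only if arithmetic means are compared. The log-normal case is not secure either, since a count can be zero (about 5% of subjects under a negative binomial with this mean and SD).
- **Type I error is not inflated.** Also correct. The harm is a greater chance of failing to show equivalence.

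**Conclusion.** The stated power is wrong. With the plan's planning values and its 90% CI rule, 156 evaluable subjects per group give about 80% power, so the risk of missing true equivalence is about 20%, twice the stated 10%. If the ratio of arithmetic mean counts is analysed, the risk is about 33 to 35%. The 80% figure assumes an unadjusted log-normal comparison and identical formulations; within an unadjusted analysis it is the favourable end, and a true ratio of 0.95 or 1.05 lowers it to about 71%. That 156 came from 10% per side is the reading that matches exactly, but it remains an inference. The conclusion on power does not depend on it.

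**What to change.** Correct section 8.1 and the synopsis together:

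- State the level as one-sided 5% for each of two tests, equivalent to the 90% CI.
- State the assumed true ratio, the formula and the analysis scale.
- State the power at 156 evaluable per group as about 80% under the log-normal assumption with a true ratio of 1, and about 65 to 67% if the ratio of arithmetic mean counts is analysed.
- Keep the 90% CI rule. Do not move to an 80% CI to preserve the 90% power figure.

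This costs wording and a less favourable stated power; it needs no extra subjects. If the sponsor does want 90% power, the log-scale requirement is 197 evaluable per arm, which is 197 / 0.9 = 218.9, so 219 randomized per arm and 657 in total against the planned 522. A ratio of arithmetic means would need about 248 to 253 evaluable per arm. Resizing is optional; correcting the statement is not.
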